10.5 Quality of Life and Health economics measures

Client Service Receipt Inventory (CSRI)²³: CSRI is a validated tool to measure total package resource use and has been used in evaluations involving service users with psychiatric problems and service users with LD. It records items such as contacts with community-based primary care, other health or social services, educational services, and outpatient and inpatient attendances. Unit costs for most of these are available. EQ-5D-Y Proxy version 1 (EuroQol, 2009): The EQ-5D -Y is a standardised measure of health status for clinical and economic appraisal, and will be completed by parents to assess their children's' health-related quality of life in their (the proxy's) opinion, as well as to explore the feasibility of measures to be used in a future health economics evaluation. It takes approximately 5 minutes to complete.

EQ-5D-Y Interviewer Administered version (EuroQol, 2009): The EQ-5D-Y is a standardised online measure of health status for clinical and economic appraisal and will be completed by adolescents (youth version) to assess their health-related quality of life, in the areas of mobility, looking after oneself, doing usual activities, having pain or discomfort and feeling worried, sad or unhappy). It will also be used to explore the feasibility of measures to be used in a future health economics evaluation.

11.0 Data collection and blinding

The two interventions consume similar interaction time between dyads and therapists. This reduces the chance of the research assistants inadvertently having group allocation revealed to them by virtue of participants' references to meeting with therapists.

The research assistants carrying out the assessments will be masked to intervention allocated and/or received. The Chief Investigator will be informed of any unmasking and corrective action in terms of training and correctly following procedures will be instigated if necessary. Treatment allocation will remain concealed until all participants have exited the trial.

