In the proposed study, half the participants will take part in the Beat-D (behavioural 16.03.2023 Version 1.4 6

activation) treatment, and half will receive usual NHS treatment. People who choose to take part will be involved for a maximum of six months. The study will take place in Birmingham. We would like to find out: i) if we can recruit participants to the study, ii) if we can collect the outcome measures iii) what people think about the treatment and research study design.

Our team is made up of researchers with expertise in working with people with LD, experts on clinical therapeutic interventions, and experts in using statistics in research. In the study centre, we have strong links with the NHS and specialist learning disabilities service.

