4.0 Study design

The proposed study is a single-centre, single-blind, feasibility randomised controlled trial (RCT) of Beat-D compared to treatment as usual, plus a qualitative investigation of adolescents', carers', and therapists' perspectives on the treatment. The design of the study is illustrated in Figure 1, and the schedule of research assessments outlined in Table 1. The researchers collecting the outcome data will be blinded to which group participants have been allocated.

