8.2 Treatment as usual

This will include the existing treatments available in NHS and social care for adolescents with LD with depression, including anti-depressants, mood stabilizers, and any available psychological interventions. Information will be collected from both groups about service supports and treatments they receive during the course of the study, to help describe treatment as usual and to inform the data collection methods for the economic element of a future trial.

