8.3 Therapist adherence to the Beat-D protocols

To establish adherence in the delivery of the Beat-D treatment by therapists, fidelity checklists will be completed after every session by the therapists and provided to the research team for analysis.

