10.4 Qualitative interviews and process evaluation

Carer and therapist interviews will be conducted according to a semi-structured interview schedule. The questions will address the participants' views and experiences of the Beat-D therapy and attention control to develop a better understanding of the change process. Design of the set of tools will take account of lessons learnt on our own and others' previous work, taking in the views of people with LD, including guidelines approved by the ESRC.

As a standard part of the Beat-D treatment protocol, therapists also complete written therapist logs at the end of each intervention session, noting their impressions of barriers to change, the successful therapy tasks and ways they adapted the approach (in accordance with the manual) to individual needs and circumstances.

Therapists will also collect routine data from the participants about their level of activity and their success in carrying out the homework tasks, along with reports from the participants about their mood that will provide evidence of the pattern of change across sessions.

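### The stated protection of assessor masking assumes similar therapist contact in both arms, but the comparator is treatment as usual with no matched contact

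*Protocol*

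**What the plan says.** Section 4.0 describes a single-blind "feasibility randomised controlled trial (RCT) of Beat-D compared to treatment as usual" and says that those who collect outcome data are masked to group. The Study Summary adds that "half will receive usual NHS treatment". Section 8.2 defines the control arm: "This will include the existing treatments available in NHS and social care for adolescents with LD with depression", with antidepressants, mood stabilisers and whatever psychological help is available given as examples.

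Section 11.0 explains why masking should survive contact with the families: "The two interventions consume similar interaction time between dyads and therapists". It continues: "This reduces the chance of the research assistants inadvertently having group allocation revealed to them by virtue of participants' references to meeting with therapists".

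Section 10.4 says that the interview questions will cover "views and experiences of the Beat-D therapy and attention control".

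On service use, section 8.2 states: "Information will be collected from both groups about service supports and treatments they receive during the course of the study". Section 10.1 puts the Client Service Receipt Inventory (CSRI) in Table 2 with the depression, anxiety, activation and quality-of-life measures, for baseline and four months.

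**The concern.** The sentence in section 11.0 would suit a trial with two therapist-delivered arms. There, hearing that a family had been seeing a therapist would tell the assessor little. Here only one arm has scheduled therapy, so the same remark is informative.

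At stake is the single-blind label and the scores that an assessor can influence. The clearest case is the CDRS-R, which section 10.2 describes as rated from a semi-structured interview and schedules at baseline and four months. Section 12.2.1 uses the outcome data for an exploratory between-arm model and for the standard deviations that will inform the next trial's sample size. There is also a risk that the unsupported rationale is carried into that trial.

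**Working it through.** The protocol gives no figure to reproduce on this point. The check sets the sections side by side.

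**1. Contact specified in each arm**

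| | Beat-D (section 8.1) | Treatment as usual (section 8.2) |
|---|---|---|
| Carer training | 1 session | none specified |
| Sessions with the dyad | 8 to 12 over about four months | none specified |
| Total specified | 1 + 8 = 9 to 1 + 12 = 13 | 0 |
| Study therapist, schedule or contact matching | therapist, manual and schedule | none |

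The phase counts in section 8.1 (4 assessment, 5 to 10 active, 2 final) add to 11 to 16, which does not agree with 8 to 12. Those figures need to be reconciled, but the comparison here is the same under either. Actual psychological contact under treatment as usual is not given. It could be anything from none to whatever local services offer, and nothing in the protocol makes it similar to Beat-D. Exclusion criterion 5 means that participants in both arms enter without current psychological therapy.

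**2. The premise against the design.** Section 11.0 needs similar contact in both arms. Sections 4.0, 8.0 and 8.2 provide for no such thing. The attention control in section 10.4 matches no arm in section 8.0. Two sections therefore describe a comparator that this trial does not have.

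**3. When the gap matters.** Section 12.1 allocates participants after baseline data are collected, so baseline ratings are not exposed. The four-month assessment is. It falls due at about the time the Beat-D sessions end.

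**4. Routes to disclosure at four months**

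- *Spontaneous remarks.* Section 10.1 describes interviews with participants, usually at home, and lets carers complete assessments with the researcher by phone. Section 11.0 addresses remarks about therapists only through the equal-contact argument.
- *The CSRI.* Section 10.5 says that it records contacts with health, social and educational services. It does not name Beat-D, but a run of recent therapy contacts would be informative. The protocol states neither an order of measures nor a separate collector.
- *The qualitative interview.* Table 1 places it at the same time point, for a subsample. Section 10.4 does not say who conducts it.

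**5. Other safeguards, and whether they close these routes**

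| Safeguard | Section | Prevents disclosure by a dyad? |
|---|---|---|
| Randomisation lists in a restricted folder | 12.1 | No; it protects the list |
| Allocation withheld from the research assistant; coordinator contacts the clinicians | 12.1 | No; it closes the staff route only |
| Unmasking reported to the Chief Investigator, with corrective action | 11.0 | No; it acts afterwards |

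**6. Extent.** With 20 participants (section 5.1) split in half (section 1.0), about 20 / 2 = 10 dyads would have Beat-D sessions that could be mentioned. That is the number exposed, not an estimate of how many would unmask the assessor.

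**The case against.** The strongest reply is that this is a wording error in a small feasibility study whose masking has other supports. Much of that stands.

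- A reader might infer that any mention of sessions identifies Beat-D. The documents do not support this. Section 8.2 allows psychological interventions within usual care, exclusion criterion 5 applies at entry only, and section 8.4.2 says that delivery is by NHS clinicians. Seeing an NHS therapist makes Beat-D likely, not certain.
- A reader might infer that no safeguard is left. Sections 11.0 and 12.1 show otherwise. What is missing is protection against disclosure by the family.
- A reader might infer that fidelity checklists unmask the assessors, because section 8.3 says that "fidelity checklists will be completed after every session by the therapists and provided to the research team for analysis". The research team is not shown to include the masked assistants, and section 12.1 already has an unmasked coordinator and restricted files. This calls for a clarification only.
- The visit order may be set in working instructions. If the CSRI comes last, it cannot affect that visit's ratings. The protocol's silence is not an error, but once the equal-contact rationale goes, the order becomes the main protection.
- Most scales are self-report or carer report, from people who know their allocation whatever the assessor knows. Assessor masking protects those less, so the consequence is concentrated on the CDRS-R.
- The study is not powered for efficacy, and none of the eight secondary objectives asks about masking. It therefore cannot be said that the trial would answer a stated feasibility question wrongly. Recording unmasking is a cheap addition, not the repair of a broken objective.

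None of this rescues the sentence in section 11.0, which remains untrue of this comparator.

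**Conclusion.** The point holds as an internal contradiction with a practical consequence. Section 11.0 relies on similar therapist time, while the protocol specifies 9 to 13 contacts in one arm and none in the other. The only stated protection against disclosure by adolescents or carers at four months has no basis in this design, and section 10.4 repeats the mismatch. Disclosure through conversation or the CSRI is likely but not certain. The size of any resulting bias cannot be derived from the documents, and no sample size or power figure is affected.

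Two assumptions remain. The first is that the masked research assistants collect the CSRI; section 10.1 implies this but does not say so. The second is that they also rate the CDRS-R. Section 10.2 refers to a clinician rater, while sections 4.0 and 11.0 put outcome assessment with masked researchers. If someone else does either task, the exposure is smaller, but the text still needs correcting. This should be fixed; it does not defeat the study's feasibility aim.

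**What to change.** 1. In section 11.0, delete the similar-contact rationale and state that therapist contact differs by arm. In section 10.4, remove the attention control.
2. At four months, complete all depression, anxiety, activation and quality-of-life measures before the CSRI, any question about treatment and the qualitative interview. Apply the order across the dyad, so that a carer's CSRI by phone does not precede the adolescent's ratings.
3. Ask dyads not to mention therapy to the assessor, in words that do not discourage adverse event reports, which section 9.3 collects at study visits.
4. Have the assessor record, after the outcome scales and before the CSRI, whether allocation was revealed and a guess at the arm. Report both by arm.
5. As a clarification only, state that fidelity checklists and therapist logs are not accessible to the masked assessors, and say who rates the CDRS-R and who collects the CSRI.

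The cost is protocol wording, a fixed visit order and one extra CRF item. No additional participants are needed.

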12.0 Statistical considerations

12.1 Randomisation

Participants will be allocated to one of two study groups using random permuted blocks. The randomisation lists will be developed by the trial statistician, who will not be involved in recruitment, data collection, or statistical analysis. The final lists will be passed to the study coordinator, who will save them in a restricted folder (i.e. not accessible by those who are to remain blind to allocation for the duration of the study period).

After obtaining informed consent and the collection of baseline information, participants will be allocated to one of the two study groups.

The research assistant will e-mail the study coordinator with the participant's screening number, age, and gender (for verification). The study coordinator will access the list corresponding to the participant's centre and assign the next available allocation to the participant. The allocation will not be revealed to the research assistant. Following this, the study coordinator will contact the clinicians to arrange subsequent study visits.

12.2 Data analysis

12.2.1 Quantitative analysis

All outcome and demographic variables will be presented descriptively using appropriate summary statistics. In addition, variables with baseline and post-intervention measurements will be analysed using mixed effects linear regression to explore potential intervention effects. Although this feasibility study is not powered to explore efficacy, the outcome data will be used to estimate the standard deviation of the data for the different outcomes and will be used to inform the sample size calculations for the next phase of this study.

12.2.2 Qualitative analysis

The interviews will be analysed using framework analysis. This is a highly structured form of qualitative data analysis initially developed by the National Centre for Social Research²⁴ and particularly suited for applied research. Rather than themes and subthemes being wholly emergent from the data, framework analysis allows the researcher to start with a set of a priori themes which are used as an initial guide to the analysis, although in the analysis these themes can be altered and new themes can emerge from the data. Framework analysis is less labour-intensive than many other types of qualitative data analysis, and allows for the systematic examination of data from relatively large samples for qualitative analysis.

For this study, the major a priori themes to begin the framework analysis will concern a number of dimensions that may inform the future uptake of the intervention in clinical practice. These will include: carers' and therapists' perspectives on the process of change; helpful and unhelpful aspects of the interventions; factors relating to the three-way working relationship and the carer-participant relationship; and

barriers and facilitative factors relating to the maintenance of the interventions after cessation of contact with the therapist.

This part of the research is not hypothesis driven. Instead, the main aim is to gain an 'insider's perspective' that will assist with the interpretation of the results and inform decision making about whether a full scale clinical trial is warranted.

13.0 Good Clinical Practice (GCP)

13.1 Ethical conduct of the study

The study will be conducted in accordance with the ethical principles that have their origin in the Declaration of Helsinki (version 9, 2008) and are consistent with Good Clinical Practice. The Research Governance Framework for Health and Community Care in Scotland (second edition, 2006), and the Department of Health Research Governance Framework for Health and Social Care will be adhered to.

A favourable ethical opinion will be obtained from an appropriate research ethics committee, and local NHS R&D approval will be obtained prior to commencement of the study.

13.2 Investigator responsibilities

The Chief Investigator is responsible for the overall conduct of the study, compliance of the protocol and any protocol amendments. In accordance with the principles of GCP, the following areas listed in this section are also the responsibility of the Chief Investigator. The responsibilities may be delegated to an appropriate member of the study staff. Delegated tasks will be documented in a delegation log and signed by all those named on the list.

13.3 Study site staff

The Chief Investigator will be familiar with the protocol and the study requirements, and will remain up to date with the principles of Good Clinical Practice. It is the Chief Investigator's responsibility to ensure that all study staff are adequately informed of the protocol and trial related duties.

The researchers and therapists involved in the study will follow the local University and NHS procedures and policies for lone workers.

13.4 Data recording

The Chief Investigator is responsible for the quality of the data recorded in the study and the databases' affiliated documentation.

13.5 Confidentiality

All evaluation forms, reports and other records will be identified in a manner to maintain participant confidentiality. All records will be kept in a secure storage area with restricted access to research staff. Study information will not be released without the written permission of the participant, except as necessary for monitoring auditing by the sponsor, sponsor's designee, regulatory authorities or the research ethics committee.

The Chief Investigator and study staff will not disclose, or use for any other purpose other than performance of the study, any data, raw record or other unpublished, confidential information disclosed to those individuals for the purpose of the study. Prior written agreement from the sponsor, or the sponsor designee, will be obtained for the disclosure of any confidential information to other parties.

13.6 Data Protection

All study staff involved with this study will comply with the requirements of the GDPR regulations with regard to the collection, storage, processing and disclosure of personal information.

Electronic data will be stored on firewalled University and NHS computers. Files will be password protected and only accessible to researchers responsible for the running of the study and the CI. All procedures for data storage, processing and management will be in compliance with GDPR regulations. All participants will be given a unique study number and no personal details will be retained. All paper records will be stored in a locked filing cabinet, with keys available only to researchers and the chief investigator. The Trial Statistician will carry out analysis. All essential documents generated by the trial will be kept in the Trial Master File.

14.0 Study conduct responsibilities

14.1 Protocol amendments

Any changes in research activity, except those necessary to remove an apparent immediate hazard to the participant, must be reviewed and approved by the Chief Investigator. Amendments to the protocol must be submitted in writing to the sponsor for approval and subsequently to the research ethics committee and local NHS Research and Development offices for approval, prior to the participants being enrolled into an amended protocol.

14.2 Study record retention

All study documentation will be kept for ten years after the end of the research and will be archived in line with standard operating procedures on archiving.

14.3 End of study

The end of the study is defined as the last participant's final visit from relevant research staff and will be reported to the sponsor, research ethics committee and NHS R&D.

Once the final report has been approved by the study funder a copy will be sent to the sponsor and NHS R&D offices. A summary report of the study will be provided to the research ethics committee within one year of the end of the study.

15.0 Reporting, publications and notifications of results

15.1 Authorship policy

Ownership of the data arising from this study resides with the sponsor. On completion of the study, the study data will be analysed, and a final report prepared.

15.2 Publication and presentations

The study report will be used for publication and presentation at scientific meetings. Investigators have the right to publish orally or in writing results of the study. Published results will not contain any personal data that could allow identification of individual participants.

Summaries of results will be sent to participants and carers after the findings have been accepted through the peer review process.

APPENDIX A - Lone Working Protocol for BEAT-D

Lone Working:

Lone workers should ensure that their team/line manager have their personal contact number, their In Case of Emergency (ICE) details and details of their car make/model and registration number (if applicable) or other travel details. It is the lone worker's responsibility to ensure that all contact details are maintained and updated.

All lone workers that are issued with mobile phones are expected to keep them charged and turned on whilst at work. Lone workers should consider putting the phone number for their CEDAR admin staff/ RA buddy in the phone so that they have quick access if required. There are a number of personal safety mobile apps which could also be considered: https://www.suzylamplugh.org/Pages/Category/app-directory

Protocol for attending a site/home visit alone:

The RAs on the BEAT-D project have shared access to their Outlook calendar so that appointment details (including the time, participant name and visit location) can be viewed by their Line Manager, admin staff and other RAs if needed.

Before a site/home visit, the RA who is completing the visit shares information with their RA buddy and LM about which participant (Participant ID) they are going to visit and where they are meeting them, whether this is in a public place or at a family home, the date and time of the meeting, and how long they anticipate that this will last. Both LM and buddy RA at the Warwick site have access to the participant databases, within which are all participant data (including home address).

On the day of the site/home visit, the RA who is completing the visit calls the other RA to confirm that they have arrived at the meeting location. If possible, the RA completing the visit can share their location with the other RA on their mobile 'phone. The RAs agree a time to call after the visit and if the RA completing the visit does not call at the agreed time then the other RA will call them to confirm that they are OK. If necessary, this can be completed when the RA completing the visit arrives home after the visit.

If the RA who is completing the visit answers the phone, then the other RA will ask if they are OK and if they need to arrange for another call to take place (if the visit has overrun). The process above is then completed at the newly arranged time.

If the RA who is completing the visit does not answer the phone after a couple of attempts, then the other RA can try to call the person/place they were visiting to establish if they are there or when they left. If no contact can be made, then the other RA must report this to their line manager or a senior member of staff who will then escalate the procedure. If there is concern then the police should be contacted.

University security should also be informed of the situation by calling [name]. University security will then respond to the incident and will liaise with emergency services as required.

If the RA completing the visit feels unsafe but cannot leave the situation, a phrase must be agreed which will be used and understood by the other RA. This phrase means that they are in difficulty and requires help, for example, "I need the red folder". This should prompt the other RA to alert a line manager who will escalate to a senior member of staff who should consider phoning the police.

Principles of Lone Working from the Warwick Clinical Trials Unit:

When lone working, staff should:

- Be alert to warning signs (body language, tone of voice)
- Carry out a '10 second risk assessment', if staff feel unsafe they should leave
- Check for evidence of pets
- On arrival assess the layout and quickest/safest exit route
- Be aware of entrances and exits
- Place themselves near an exit
- Be aware of the positioning of items which could be potential weapons
- In multi-storey buildings consider safety when choosing lifts or staircases
- Remain calm and focussed under no circumstances put themselves at risk
- Consider the distance that they are travelling each day. Staff should liaise with their line managers about reasonable distances to travel in a day.
- Remember that if they are in any doubt about their safety, to leave the situation
